Principal investigators and participating centers	[name] Psychiatry Hospital of Santa Creu i Sant Pau [name]: Hospital del Mar. Barcelona [name] : Reina Sofia University Hospital. Cordova [name] : Parc Taulí University Hospital [name] : A Coruña University Hospital [name]: Gregorio Marañoñ University Hospital, Madrid [name]: University of Navarra Clinic. Pamplona [name] : Hospital Clínic, Barcelona [name]: León University Assistance Complex [name]: Valle del Nalón Hospital. Asturias [name]: Vigo University Hospital Complex, Pontevedra [name]: Arnau de Vilanova University Hospital. Lleida [name]: San Carlos Clinical Hospital, Madrid [name]: Bellvitge University Hospital [name]: Hosp. Univ. Virgen del Rocio of Seville [name]: Regional University Hospital of Malaga

	
[name]: Germans Trias i Pujol University Hospital. badalona [name] : Virgen de la Macarena Hospital, Málaga [name] : Hospital Mutua de Terrassa, Terrassa. [name] : Son Llàtzer Hospital, Majorca [name]: Trueta Hospital, Girona [name] : University Hospital of the Canary Islands, Tenerife. [name] :H. Virgin of Light-Cuenca [name] : H. University Virgen de la Victoria-Málaga. [name] : Reina Sofia-Córdoba University Hospital [name] : Viladecans Hospital, Barcelona [name] : H. University [name]: [name] : H. San Carlos Clinic in Madrid [name] : H. de Reus [name] : H. General of Vic

Reference ethics committee	CEIM of the Hospital de la Santa Creu i Sant Pau
Main goal	To study the evolution after bariatric surgery in patients with obesity and schizophrenia
Design	Multicenter retrospective case control study.
Disease under study	Schizophrenia and Obesity
Methodology	Retrospective observational study
Study population and total number of subjects	Cases: Patients with schizophrenia and obesity undergoing bariatric surgery. (number: all cases collected within the GOSEEN group). Controls: Patients without psychiatric pathology matched by age, sex, BMI and type of surgery and in a 4:1 ratio to cases.
Calendar. Expected duration of the study.	12 months
ethical considerations	Informed consent will be obtained from patients who are currently being followed up at the reference centers.
Funding source	Not precise

2. THEORETICAL FRAMEWORK. PROBLEM STATEMENT:

Background

Obesity affects approximately 45-55% of patients with schizophrenia (1). Weight gain in these patients may be due to different factors such as the use of antipsychotic drugs with an unfavorable metabolic profile, the coexistence of sleep disorders or negative cognitive symptoms that often translate into a more sedentary lifestyle and alterations in eating behavior, among others (2). The coexistence of obesity and its comorbidities in this group of patients significantly worsens both their physical and mental health (3). In fact, cardiovascular disease is one of the main causes of mortality in patients with schizophrenia (4).

Lifestyle interventions, while they may be effective in people with schizophrenia (5), often fall short of achieving weight goals. At present, obesity surgery represents the most effective treatment in terms of weight loss and resolution of comorbidities, being indicated in cases of patients with a body mass index (BMI) > 35 kg/m² with comorbidities or BMI > 40 Kg/m² with/without comorbidities. However, the access of patients with schizophrenia to bariatric surgery techniques is usually limited by different factors such as fear of a possible worsening of the underlying disease, or a lower weight loss in this population, among others. In addition, clinical practice guidelines recommend that all patients with psychiatric pathologies be evaluated in a regulated manner prior to surgery (6), although the content of this evaluation and the criteria for declining or accepting surgery are not clear. Although the course of schizophrenia is variable and its symptoms may be stable without being a clear contraindication for bariatric surgery, in actual practice, a considerable number of professionals contraindicate bariatric surgery in the presence of a psychotic disorder (7).

For these reasons, data on the efficacy of bariatric surgery in patients with schizophrenia are scarce and limited to very small case series with short-term follow-up (2,8,9). Our objective is therefore to carry out a multicenter retrospective study that allows us to study the long-term evolution after bariatric surgery in a large series of patients, focusing not only on weight evolution but also on the long-term evolution of psychiatric pathology.

Justification

It is necessary to have information about the prognosis of subjects with severe obesity and schizophrenia who undergo bariatric surgery. This knowledge will make it possible to establish clear guidelines for action in these cases.

Research questions

What is the long-term outcome after bariatric surgery in subjects with schizophrenia?

Hypothesis

Bariatric surgery in subjects with schizophrenia leads to an improvement in weight and cardiometabolic comorbidities similar to that of subjects without schizophrenia

3. GOALS:

Main goal:

To study the short (first year after bariatric surgery) and long-term (up to 5 years of follow-up after bariatric surgery) evolution in terms of weight loss of patients with obesity and schizophrenia who underwent bariatric surgery in Spain and compare it with the evolution of patients without psychiatric disorder.

Secondary objectives:

- Determine the casuistry of patients, with special interest in the characteristics of the underlying psychiatric pathology (years of evolution, clinical stability criteria, pharmacological treatment...).
- To Analyze the evolution of obesity comorbidities.
- To Analyze the evolution of psychiatric pathology after bariatric surgery: (decompensation, drug treatment...)
- To analyze the frequency of early (<30 days post-surgery) or late (>30 days post-surgery) post-surgical complications.

4. METHODS:

Study design

Retrospective case-control study.

Study population. Inclusion, exclusion criteria

Cases:

Inclusion) Both criteria must be met:

- 1.- Patients with severe obesity undergoing bariatric surgery and with follow-up in Spanish territory.
- 2.- Patient with schizophrenia or schizoaffective disorder.

Exclusion)

Subjects who do not meet any of the two inclusion criteria

Controls: in a 4:1 ratio with cases

Inclusion) Both criteria must be met:

- 1.- Patients with severe obesity undergoing bariatric surgery and with follow-up in Spanish territory.
- 2.- Absence of psychiatric pathology
- 3.- Paired with the cases by age, sex, BMI before surgery and type of surgery.

Exclusion)

Subjects who do not meet any of the two inclusion criteria

Definition of variables

Main variables:

- weight
- size
- BMI

- TWL (total weight loss)
- EWL (excess weight loss)

Secondary variables:

- Age, ethnicity, educational level
- Type of surgery
- psychiatric dx
- Years of evolution of the psychiatric disorder at the time of IQ
- Psychiatric drug treatment, lithium, medication load.
- Number of psychiatric admissions prior to IQ.
- Number of psychiatric admissions/psychiatric emergencies after surgery (relapses): In-hospital relapses, Relapses < 30d, relapses during follow-up.
- Criteria for approval of surgery (in each center).
- Biochemical parameters: glucose, HbA1c, total cholesterol, triglycerides, HDL, LDL.
- Early and late postoperative complications and death of the patient.
- Presence of diabetes, arterial hypertension, dyslipidemia, OSAS and liver disease and treatments for these pathologies.
- Adherence to follow-up in endocrinology and dietetics (Number of visits attended/Number of scheduled visits)
- Lost to follow-up.

The collection of variables will be carried out pre-surgery and 1 month, 6 months, 12 months and subsequently annually until a maximum of 5 years of follow-up.

Expected sample size

All cases detected in Spanish territory

The minimum number of cases expected will be 10 patients based on the low casuistry of the problem. The number of patients in the control group will be x4 that in the study group.

Methodology. Information sources

The study population will be identified in each center in the usual specialty consultations or by searching the databases of each center. Review of medical records in search of the specified variables (retrospective observational study).

Data Management and Analysis

The coordinating researcher (Dra [name]) will be responsible for the creation of the database and its exploitation. The database will be created in Excell format and the SPSS program will be used for statistical analysis. The statistics will be mainly descriptive. For cases in which it is decided to compare groups, normality tests will be used to establish the behavior of the variables and parametric/non-parametric tests will be used as appropriate.

Data collection

The researcher will guarantee the accuracy and integrity of the data, as well as all the reports that are required. The data included in the Data Collection Notebook (CRD), which are derived from source documents, will be consistent with those documents or otherwise the discrepancies will be justified.

The researcher will keep the study documents until at least 5 years after completion. At the request of the monitor, auditor, ethics committee or health authority, the researcher will have available all the files related to the study, allowing direct access to the data or source documents for monitoring, auditing, review by the ethics committee, as well as the inspection of the trial by the competent authorities.

Limitations of the design, the source of information and the methods of analysis

The main limitation of the study is its retrospective nature. However, the study design is adequate given the low frequency of the pathology.

5. WORK PLAN (tasks, milestones and timeline of the study):

month 1

Elaboration of the protocol. Edition of study materials. base design data. Meeting of researchers to resolve doubts. Preparation of the logistical aspects for the start-up of the study.

month 2-4

Presentation to the ethics committee.

month 4-8

Registration in ISRCTN

Start of study. Patient identification. Collection and introduction of data.

month 8-12

Data purification and analysis. Meeting of researchers to discuss the results and close the study. Preparation of the final report. Preparation of a manuscript for publication of the results.

Duration: 12 months

6. ETHICAL ASPECTS:

Research benefit-risk assessment

The present investigation, given its retrospective nature, does not pose a risk to the study patients. The expected benefits of it are a better knowledge of the risks and benefits of bariatric surgery in subjects with schizophrenia. This will allow in the future to establish the risk-benefit of bariatric surgery in these patients.

Ethical considerations, on information to the subjects and informed consent

The study will be carried out strictly following the international ethical recommendations for medical research in humans. The investigator will be responsible for ensuring that the study is carried out in accordance with the standards contained in the Declaration of Helsinki.

Before starting the study, the Ethics Committee of the Hospital de la Santa Creu i Sant Pau must approve the study protocol, the information that will be given to the subject and the informed consent model that will be used.

The CEIC will be informed of any subsequent amendment to the protocol and its opinion should be requested in the event that a new evaluation of the ethical aspects of the study is necessary.

It is the responsibility of the investigator to obtain the informed consent of the patient. The patient will not be able to participate in any study-specific procedure without obtaining their consent, or that of their legal guardian/family member when the patient is unable to give consent due to their clinical situation.

Before including any subject in the study and before obtaining informed consent, the investigator or the person designated by the investigator will explain to the potential participating subject or their legal guardian/family member the objectives, methods, and potential risks of the study and any inconvenience it may cause. The explanation about the nature, scope and possible consequences of the study will be made in an understandable language.

The prospective participant or their legal guardian/family member should have time to consider their decision to participate in the study, and have the opportunity to ask questions. After this explanation, and before entering the study, the consent must be properly recorded by the signature of the subject or their legal guardian/family member. Given the retrospective nature of the study, it is likely that some patients to be included have died or are no longer seen at their referral center. In this case, informed consent will not be obtained, but the research team undertakes to verify that there is no record of the subjects' express opposition in the clinical history and to comply with the confidentiality regulations.

In addition, since the use of pseudonymized personal data for biomedical research purposes requires technical and functional separation between the research team, and those who perform the pseudonymization and keep the information that enables re-identification, the person who performs the pseudonymization for this study does not will be part of the research team.

For access to the pseudonymous data, an express commitment of confidentiality and not to carry out any re-identification activity is sent, and that specific security measures will be adopted to avoid re-identification and access by unauthorized third parties.

The Model Patient Information Sheet and the Consent Form are presented as an Annex.

Considerations on the treatment of biological samples

Does not apply

Data confidentiality

Regarding the confidentiality of the study data, the provisions of Organic Law 3/2018, of December 5, on the Protection of Personal Data and Guarantee of Digital Rights and the General Regulation (EU) on Data Protection will be followed. 2016/679.

Interference with physician's prescribing habits

As it is a retrospective study, there will be no interference with the prescribing habits of the doctor.

7. PLANS FOR DISSEMINATION OF RESULTS:

An oral presentation is planned within the framework of the Congress of the Spanish Society of Endocrinology and Nutrition. The results will be published in a journal of the Specialty, prioritizing those in the first quartile.

8. RESOURCES FOR CARRYING OUT THE STUDY AND FINANCING:

This study will ask the Spanish Society of Endocrinology and Nutrition (SEEN) for funding to cover the possibility of publication fees in an online journal.

9. MODIFICATIONS TO THE PROTOCOL:

Any modification to the study protocol will always take the form of a written amendment or addendum. For its formalization, the approval of all the people responsible for the study will be required. In the case of relevant modifications, the express approval of the Clinical Research Ethics Committee will be requested.

10. PRACTICAL CONSIDERATIONS:

Start, follow-up and end reports

The start of the study will be notified to the ethics committee. Subsequently, annual monitoring reports will be sent.

After obtaining the conclusions of the study, a final report will be prepared and presented to the ethics committee.

11. BIBLIOGRAPHY:

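### The hypothesis is that improvement is similar in the two groups, but the comparison wording in the analysis section is conditional and its tests, read ordinarily, cannot show similarity

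*Protocol*

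**What the plan says.** Section 2 of the protocol, under Hypothesis, states a single hypothesis: "Bariatric surgery in subjects with schizophrenia leads to an improvement in weight and cardiometabolic comorbidities similar to that of subjects without schizophrenia". The main goal in section 3 is to study weight loss over the first year and up to five years after surgery in the cases and to "compare it with the evolution of patients without psychiatric disorder". Four controls per case, matched on age, sex, pre-surgery BMI and type of surgery, are collected.

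Section 4, Data Management and Analysis, describes the analysis in three statements. First, "The statistics will be mainly descriptive". Second, "For cases in which it is decided to compare groups, normality tests will be used to establish the behavior of the variables". Third, "parametric/non-parametric tests will be used as appropriate".

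Section 4, Expected sample size, plans to take every case found and adds: "The minimum number of cases expected will be 10 patients based on the low casuistry of the problem". This is a feasibility count. No significance level, power, SD or effect size is attached to it.

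**The concern.** A hypothesis of similarity and a test for a difference are different questions. A difference test starts from no difference and asks whether the data contradict it. If they do not, the reason may be that the groups are alike or that the study is small. The p-value alone cannot tell these apart; an interval for the difference can.

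The direction matters here. The Background lists "a lower weight loss in this population" among the factors that limit these patients' access to surgery, so a deficit is what readers will want excluded. The Justification says of the results: "This knowledge will make it possible to establish clear guidelines for action in these cases". If a non-significant comparison from few cases were reported as similar weight loss, the data might still be compatible with the deficit in question.

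**Working it through.** **1. The sections side by side.**

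| Place in protocol | What it fixes |
|---|---|
| Section 2, Hypothesis | Improvement similar to controls, for weight and for comorbidities |
| Section 3, Main goal | Weight loss compared with controls |
| Section 3, Secondary objectives | Evolution of comorbidities analysed; no comparison with controls mentioned |
| Section 4, Data Management and Analysis | Mostly description; tests where a comparison is decided on, chosen after normality tests |

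The last row does not exempt the main-goal comparison from the condition. It also names no form of result, such as an interval for the difference, that could support the first row.

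**2. The plan's own figure.** 10 cases at 4:1 gives 4 × 10 = 40 controls, 50 patients in all. There is no power calculation to reproduce.

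**3. What a difference test can and cannot say at that floor.** Inputs from the protocol: 10 cases and 4 controls per case. Assumed, because the protocol gives no values: a common SD, used as the unit; a two-sided 5% level; independent groups (matching ignored); complete data.

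- Standard error = SD × √(1/10 + 1/40) = SD × √0.125 = 0.354 SD.
- 95% CI half-width = t(0.975; 48 df) × SE = 2.011 × 0.354 = 0.71 SD.
- For a true deficit of 0.5 SD, the noncentrality is 0.5/0.354 = 1.41. Power from the noncentral t distribution is 0.283, so the chance of a non-significant result is 1 − 0.283 = 0.717, about 72%.

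For example, an observed deficit of 0.70 SD with a sample SD of 1 has a 95% CI from −0.70 − 0.71 = −1.41 to −0.70 + 0.71 = +0.01. That is non-significant, yet it is plainly not evidence of similarity.

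**4. How this changes with more cases.** Ten is a minimum, so the same formulas were applied to larger numbers (assumed, 4:1).

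| Cases / controls | SE (SD) | 95% CI half-width (SD) | Chance a true 0.5 SD deficit is non-significant |
|---|---|---|---|
| 10 / 40 | 0.354 | 0.71 | 72% |
| 20 / 80 | 0.250 | 0.50 | 49% |
| 40 / 160 | 0.177 | 0.35 | 20% |

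**5. Allowance for matching.** If outcomes within a matched set have correlation ρ, SE = SD × √((1 − ρ) × 1.25/n), with 4n − 1 df. At 10 cases, an assumed ρ of 0.2 gives 2.023 × 0.316 = 0.64 SD, and 0.4 gives 2.023 × 0.274 = 0.55 SD. Matching narrows the interval but does not change the conclusion at the floor.

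**The case against.** Several points on the other side are fair.

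- **The weight comparison is already promised.** The main goal commits to it and the matched controls exist to serve it. The conditional phrase may only mean choosing among the many listed variables, some of which (psychiatric diagnosis, years of psychiatric illness, relapses) have no counterpart in controls. A reader might infer that the protocol leaves its main comparison optional. The text does not establish that. What stands is that the analysis wording does not exempt the main-goal comparison, so the sections are in tension.
- **The protocol never says that non-significance will be read as similarity.** A reader might infer that it will, but no sentence says so, and no significance threshold is given. The test wording is loose enough that an interval or a pair of one-sided tests could fit it. What stands is that the ordinary reading is a difference test, and nothing guards against the misreading.
- **Margin, primary variable and time point may sit in the SAP.** The SAP is not available here, and their absence from the protocol is not held against it. The point concerns the mismatch between statements that the protocol does make.
- **The study is mainly descriptive, and *similar* may be only an expectation.** If so, estimation is the natural form for the hypothesis, which is the simpler of the two remedies below.
- **Ten cases is a floor.** The plan is to collect all cases from a long list of centres. The figures illustrate the risk and do not predict this study's precision.

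**Conclusion.** The concern holds as a mismatch within the protocol: a hypothesis of similarity and a comparative main goal are paired with an analysis paragraph whose comparison is conditionally worded and whose tests, read ordinarily, address a difference. This conclusion rests on the text and needs no calculation.

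The numbers show only why it matters when few cases are found. At 10 versus 40, the half-width is about 0.71 SD and a true 0.5 SD deficit is missed about 72% of the time. Both rest on an assumed common SD as unit, a two-sided 5% level, unpaired groups and complete data. The 0.5 SD deficit is itself an assumed value, not one that the protocol calls important. With 40 cases the chance of missing it is about 20%.

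A reader might go further and infer that the study cannot answer its question. The documents do not support that: the final number of cases is open, and descriptive estimates with intervals would bear directly on the hypothesis. The wording should be corrected before data extraction; the design need not change.

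**What to change.** In section 4, Data Management and Analysis:

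1. State that the main-goal comparison of weight loss between cases and controls will be done.
2. Report it as the case-minus-control difference with a 95% CI.
3. State that a non-significant test will not be read as evidence of similarity.
4. Treat differences in comorbidities as supportive estimates with 95% CIs.

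In section 2, preferably reword the hypothesis as estimation of the difference between the groups. Otherwise keep the similarity claim, but make it only if the interval meets a margin that is clinically justified and fixed before data extraction, and report the result as inconclusive if it does not.

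The margin value, the primary weight variable and the time point may be left to the SAP.

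The change is to wording only, with no new patients, procedures or data. The downside is that with few cases the study may have to report an inconclusive result, and the margin route obliges the investigators to justify a margin in advance.

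### Late complications are set as a frequency over a window with no common end, and the variable list names no dates from which observation time could be measured

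*Protocol*

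**What the plan says.** Section 3 (Goals, Secondary objectives) asks "To analyze the frequency of early (<30 days post-surgery) or late (>30 days post-surgery) post-surgical complications". It gives no denominator and no end to the late window.

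Section 4 (Methods) fixes the rest:

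- **Eligibility:** "Patients with severe obesity undergoing bariatric surgery and with follow-up in Spanish territory". No minimum length of follow-up and no range of surgery dates is given.
- **Controls:** "Paired with the cases by age, sex, BMI before surgery and type of surgery". Surgery date and length of follow-up are not matching factors.
- **Safety variables:** "Early and late postoperative complications and death of the patient". Separate entries cover visits attended out of visits scheduled, and "Lost to follow-up".
- **Timing:** "The collection of variables will be carried out pre-surgery and 1 month, 6 months, 12 months and subsequently annually until a maximum of 5 years".
- **Analysis:** "The statistics will be mainly descriptive". Where groups are compared, parametric or non-parametric tests follow a check of normality. No person-time or time-to-event method is named.

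The variable list names no date of surgery, complication, death or last contact. The evaluation scheme in Appendix 1 puts all retrospective data collection in a single column, V0.

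**The concern.** A proportion with an event is easy to read when everyone is watched for the same time. That is nearly so for the first 30 days. It is not so for the late window, where one patient may contribute a few months and another almost five years. A simple late frequency then reflects both the risk and how long people were watched.

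This matters in two ways. In the patients with schizophrenia taken alone, a late frequency over unequal and unstated follow-up understates 5-year risk, although the study asks about long-term outcome and section 6 gives better knowledge of the risks and benefits of surgery as its expected benefit. If the late frequency is also set against that of the controls, any difference in follow-up enters the comparison as though it were a difference in risk.

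**Working it through.** The protocol gives no event rate, no loss rate and no calculated figure for complications, so there is no number to reproduce. Its only relevant counts are the minimum of 10 cases and the 4:1 ratio, giving 10 × 4 = 40 controls.

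**What the schedule can recover.** Collection points are at 1, 6 and 12 months and then yearly. A patient's last observation, or the timing of a late event, can be placed between two of these points: within 5 or 6 months in the first year, and within 12 months after that. Blank later time points do not by themselves separate a patient who stopped attending from one operated on too recently to have reached them. The loss variable helps, but it is not a date.

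**Size of the effect (assumed inputs).** Assume a constant rate h of first late complication from day 30, and follow-up T years since surgery. The expected crude late proportion is

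p = 1 − exp(−h × (T − 30/365.25)).

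Example with h = 0.05 per year in both groups:

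- T = 2: 1 − exp(−0.05 × 1.918) = 9.1%
- T = 4: 1 − exp(−0.05 × 3.918) = 17.8%
- ratio = 0.51

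The table gives the range. The true rates are equal in every cell; each cell shows the two crude proportions and their ratio.

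| Rate per 100 patient-years | 4 v 5 years | 3 v 4 years | 2 v 4 years | 1 v 5 years |
|---|---|---|---|---|
| 2 | 7.5% v 9.4%, 0.80 | 5.7% v 7.5%, 0.75 | 3.8% v 7.5%, 0.50 | 1.8% v 9.4%, 0.19 |
| 5 | 17.8% v 21.8%, 0.82 | 13.6% v 17.8%, 0.76 | 9.1% v 17.8%, 0.51 | 4.5% v 21.8%, 0.21 |
| 10 | 32.4% v 38.8%, 0.83 | 25.3% v 32.4%, 0.78 | 17.5% v 32.4%, 0.54 | 8.8% v 38.8%, 0.23 |

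With 5 v 5 years the ratio is 1.00. The ratio depends mainly on the two follow-up times and little on the rate. Swapping the groups inverts it.

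**A real difference can be hidden.** If the group followed for 2 years has twice the rate of the group followed for 4 years (0.10 against 0.05), the crude proportions are 17.5% and 17.8%, ratio 0.98. At 4 v 5 years the same doubling shows as 32.4% v 21.8%, ratio 1.49.

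**One group alone.** At 5 per 100 patient-years, follow-up of 2 years gives 9.1% where the 5-year figure is 21.8%. That is 9.1/21.8 = 0.42 of it.

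**After the change.** Expected time at risk to first event is p/h per patient, so events divided by time at risk is p ÷ (p/h) = h whatever T is. Equal rates then give a ratio of 1.00, provided that leaving follow-up is unrelated to risk.

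**Precision.** With h = 0.05 and 2 v 4 years, expected patients with an event are 10 × 0.091 = 0.9 cases and 40 × 0.178 = 7.1 controls.

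**The case against.** The strongest case against is that the protocol states nothing false. The word used for the measure does not rule out a rate per patient-year, and choosing a denominator is commonly left to a SAP, which is not shown here. This stands: the lack of a named method would not be a point by itself. What remains is the open window and the variable list. A SAP can choose a denominator, but it cannot fully recover dates that the chart review did not abstract. The data collection notebook is also not shown and may already hold them; if so, only the reporting part is left.

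Five stronger readings are tempting and are not supported.

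- **Observation time goes unrecorded.** It does not. A patient who left at 6 months has no entries from month 12 and can be flagged as lost, unlike one seen to year 5. The record is coarse, not absent.
- **Deaths are to be reported as a frequency.** The objective covers complications only. Death is a listed variable with no stated summary.
- **A biased comparison of complications is prescribed.** The stated comparison with controls belongs to the weight-loss goal, and the hypothesis concerns weight and cardiometabolic comorbidities. Other comparisons are made only where it is decided to make them.
- **The cases will look falsely safe.** No document says which group is followed for less time. With equal follow-up there is no bias between groups, and with shorter follow-up in controls it reverses.
- **The ethics section proves truncated follow-up.** Section 6 says "it is likely that some patients to be included have died or are no longer seen at their referral center", but this concerns who can be asked for consent now. A patient operated on long ago may no longer attend and still have five complete years on file.

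It is also fair that sampling error will dominate a comparison at the minimum of 10 cases. That limits what any measure can show, but it does not make the crude proportion easier to interpret.

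**Conclusion.** The point holds as a cheap improvement to a secondary safety objective. The protocol fixes a late window without a common end, allows follow-up of any length up to 5 years, does not balance it between groups, and lists no dates. A simple late frequency would understate 5-year risk where follow-up is short. If compared between groups with different follow-up, it would favour the group observed for less time, in a direction that the documents do not reveal.

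Under equal true rates the distortion is about 0.8 for 4 v 5 years and about 0.5 for 2 v 4 years. These figures rest on an assumed constant rate and assumed follow-up times; none comes from the protocol. The 30-day proportion is largely unaffected, and the point does not touch the weight-loss goal.

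**What to change.** In section 4 (Definition of variables), add four dates: surgery, each late complication, death, and last contact. In section 3 or the analysis section, state that:

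- early complications are reported as a simple proportion over 30 days;
- length of follow-up is reported by group;
- late complications, and deaths if they are summarised, are reported per patient-year or as cumulative incidence at fixed times such as 1 and 5 years, which match the protocol's own short- and long-term horizons.

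The cost is slightly more abstraction from records already under review. It is best done before collection starts, because all retrospective data are gathered in one pass and adding dates later means reopening charts at many centres. Estimates will stay imprecise if there are only about 10 cases, and a rate per patient-year does not correct for patients leaving follow-up for reasons linked to their risk.
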